#### 4.4 FOLLOW-UP PHASE

The duration of follow-up depends on whether subject experiences virologic failure.

- Subjects who experience virologic failure within the Treatment Phase will be assessed every 4 weeks until viral suppression is achieved (i.e., plasma HIV-1 RNA levels decline to < 50 copies/mL). Additionally, virologic failure subjects will return to clinic for long-term follow-up at 6 months and at one year from the time of the Virologic Failure (VF) Visit.

- Subjects who do not experience virologic failure at the end of the Treatment Phase, will be assessed every 2 weeks for total of 4 weeks.

#### 4.4.1 Follow-Up Visits

##### 4.4.1.1 Short-Term Follow-Up Visits

###### 4.4.1.1.1 Virologic Failure Subjects

Subjects who experience virologic failure during the Treatment Phase will be assessed every 4 weeks until the viral suppression is achieved (i.e., plasma HIV-1 RNA levels decline to < 50 copies/mL).

The following assessments will be performed at each follow-up visit (VF-FU1, VF-FU2, VF-FU3 etc.), unless otherwise specified:

- Assess for any Adverse Events and changes in Concomitant medications (see [Section 9](#) and [7.5](#)),
- Symptom-directed physical examination (see [Section 7.6](#)),
- Vital Signs (see [Section 7.9](#)),
- Collection of Blood Specimens (see [Section 7.10](#)) for
  - Plasma HIV-1 RNA level
  - TruCount T Assay
  - Anti-idiotypic antibodies to PRO 140 (at Virologic Failure - FU1 and Non Virologic Failure - FU2)
- Continue previous antiretroviral regimen or an alternative regimen selected by treating physician

###### 4.4.1.1.2 Non Virologic Failure Subjects

Subjects who do not experience virologic failure at the end of the Treatment Phase, will be assessed every 2 weeks for total of 4 weeks.

The following assessments will be performed at each follow-up visit (NVF-FU1 and NVF-FU2 visits), unless otherwise specified:

- Assess for any Adverse Events and changes in Concomitant medications (see [Section 9](#) and [7.5](#)),
- Symptom-directed physical examination (see [Section 7.6](#)),
- Vital Signs (see [Section 7.9](#)),

- Collection of Blood Specimens (see [Section 7.10](#)) for
  - Plasma HIV-1 RNA level
  - TruCount T Assay
  - Anti-idiotypic antibodies to PRO 140 (at Non Virologic Failure - FU2)
- Continue previous antiretroviral regimen or an alternative regimen selected by treating physician

#### 4.4.1.2 Long-Term Follow-Up Visits

Additionally, subjects who experience virologic failure will also return to clinic for the long-term follow-up at 6 months and at one year from the time of the Virologic Failure Visit.

The following assessments will be performed at VF-6mFU and VF-12mFU visit, unless otherwise specified:

- Assess for any Adverse Events and changes in combination antiretroviral therapy (see [Section 9](#) and [7.5](#))
  - **Note:** *Only SAEs and any AE that is considered possibly or probably or definitely related to the study treatment by the Investigator will be captured during the long-term follow-up phase.*
- Collection of Blood Specimens (see [Section 7.10](#)) for
  - Plasma HIV-1 RNA level
  - TruCount T Assay
  - HIV Drug Resistance Assay (GenoSure Prime or PhenoSense GT/Integrase)
  - HIV Trofile® DNA or RNA Assay
  - HIV PhenoSense Entry® Assay

## 5 SUBJECT COMPLETION AND WITHDRAWAL

### 5.1 SUBJECT COMPLETION

- A subject who completes the 48-week Treatment Phase and 4-week Non-Virologic Failure Follow-Up Phase will be considered as having completed the study.
- A subject who experiences virologic failure during the 48-week Treatment Phase, and undergoes the Virologic Failure (VF) Visit assessments and is followed up until viral suppression is achieved and complete Virologic Failure – 12 month Follow-Up (VF-12mFU) Visit, will be considered as having completed the study.

### 5.2 SUBJECT WITHDRAWAL

A subject who enters the Treatment Phase but does not complete the study, as defined in [Section 5.1](#), is considered to have prematurely withdrawn from the Study.

All subjects have the right to withdraw at any point during treatment without prejudice to future care. It will be documented whether or not each subject completed the clinical study. If for any subject, study treatment or observations were discontinued, the reason(s) will be recorded.

The Investigator can discontinue a subject at any time if it is considered medically necessary.

In addition, subjects WILL be withdrawn from the study, in consultation with the Medical Monitor and the Investigator, if any of the following are met:

- A subject is significantly non-compliant with the requirements of the protocol.
- The Investigator determines that it is in the best interest of the subject.
- Subject chooses to withdraw or is withdrawn due to an adverse event
- Recurring Grade 2 study drug injection related AE at two consecutive visits
- Occurrence of Grade 3 study drug injection related AE
- A subject becomes pregnant

**Note:** *The pregnancy will be followed to term for safety follow-up. Relevant safety information collected after the study has completed will be reported as supplemental information.*

- Discontinuation of study by Sponsor

Premature withdrawal from the study MAY occur if, in consultation with the Medical Monitor and the Investigator, any of the following are met:

- A subject is treated with a prohibited medication.

- Major protocol violation

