**Table 4-6: Part 2: Single-Arm, Open-label Treatment Phase [Group B]**

Study Drug	Dosage Form	IP concentration	Dosing Frequency and Amount	Route of Administration
PRO 140 700mg	Parenteral solution	175 mg/mL	2 injections of PRO 140 (2 X 2 mL/inj.) up to Week 48	SC injection

Group A or Group B subjects that do not elect to participate in Part 2 of Treatment Phase and all Group C subjects who experience virologic failure (defined as two consecutive HIV-1 RNA levels of  $\geq 200$  copies/mL) at any time during the Treatment Phase will undergo the Virologic

Failure (VF) Visit assessments and then exit the Treatment Phase to enter the Follow-up Phase of the study.

Subjects who do not experience virologic failure will enter the Follow-up Phase of the study at the end of 48-week Treatment Phase.

All study subjects will re-initiate their previous antiretroviral regimen or an alternative regimen selected by their treating physician:

- One week prior to the end of 48-week Treatment Phase, or
- Anytime during the Treatment Phase, if virologic failure occurs or have met any other criteria for discontinuation of study treatment as specified in [Section 5.2.1](#) of the protocol. Subjects will be allowed to continue PRO 140 monotherapy while waiting for new ART regimen to be constructed by the Investigator.

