**Note:**

- Subjects may return to clinic for an additional blood draw in-between the clinic visits for plasma HIV-1 RNA levels, per the discretion of the Investigator.
- Virologic failure is defined as two consecutive levels of  $\geq 200$  copies/mL.
  - Subjects in Group A that experience virologic failure have option of re-initiating ART regimen or participating in Part 2 of Treatment Phase and receive higher dose of PRO 140 (525mg SC) weekly injection for remainder of 48-week Treatment Phase or until subsequent virologic failure event after viral re-suppression on higher dose.
  - Subjects in Group B that experience virologic failure have option of re-initiating ART regimen or participating in Part 2 of Treatment Phase and receive higher dose of PRO 140 (700mg SC) weekly injection for remainder of 48-week Treatment Phase or until subsequent virologic failure event after viral re-suppression on higher dose.
- Subjects who meet any criteria (other than virologic failure) for discontinuation of study treatment as specified in [Section 5.2.1](#) of the protocol, will undergo T48 Visit assessments and enter the Follow-up Phase of the study.
- Subjects who do not experience virologic failure will enter the Follow-up Phase of the study at the end of 48-week Treatment Phase.

Visits during the Treatment Phase will commence on T1, i.e. the date of first treatment, with weekly visits ( $\pm 3$  days) thereafter. The first Treatment Visit (T1) will take place as soon as HIV-

1 viral tropism, genotype and phenotype resistance results are available for review by Investigator, within 6 weeks of the Screening Visit.

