### 7.5.1 Excluded Medications and Therapies

1. Use of concomitant antiretroviral therapy is NOT allowed during the Treatment Phase of the study EXCEPT for one week overlap of existing retroviral regimen and PRO 140 at the beginning of the study treatment and also one week overlap at the end of the treatment in subjects who do not experience virologic failure. Subject is allowed to re-initiate antiretroviral therapy during the Treatment Phase, if virologic failure occurs or if subject meets any other criteria for discontinuation of study treatment as specified in [Section 5.2.1](#) of the protocol.
2. Use of oral or parenteral corticosteroids (> 5 mg/day) is NOT allowed during the study, with the following exceptions:
  - Use of chronic systemic corticosteroids at replacement doses (e.g., < 5mg/day prednisone) AND use of inhaled, nasal, or topical steroids are allowed.

- Use of short course of systemic corticosteroids (Medrol pack) after T2 will only be allowed with prior approval from the sponsor.
- 3. Use of radiation or cytotoxic chemotherapy, immunosuppressants and immunomodulating agents (e.g., interleukins, interferons) or agents with known anti-HIV activity (i.e., hydroxyurea, foscarnet) are NOT allowed during the study.
- 4. Use of any non-FDA approved/investigational therapy

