### 9.1.8 SC Injection-related Events

SC and IV injections of concentrated protein materials can be associated with injection-related AEs that impact the ability to safely and successfully deliver the drug. Local injection-site reactions may include pain/discomfort, induration, erythema, nodules/cysts, pruritus, ecchymosis, etc. For SC injections, bleeding, absorption of the drug, leakage of drug, and induration at the local injection site can be additional complications. Other AEs that are common to monoclonal antibody-based therapies are chills, headache, backache, malaise, fever, pruritus, rash, nausea, tingling, and hypertension.

SC injection-related events will be monitored according to the guidelines provided in [Section 17.2](#) (Division of AIDS Table for Grading the Severity of Adult and Pediatric Adverse Events [DAIDS AE Grading Table]). Injection-site reactions thought to be directly related to the injection are considered to be AEs of special interest, and a separate guideline for the acquisition of data related to this AE of special interest is provided in [Section 17.3](#).

For subjects who develop grade 1 event or first occurrence of grade 2 event, continue therapy as per protocol. If a subject chooses to discontinue study treatment, the site should notify the protocol team leadership, and encourage the subject to complete any remaining study visits until the toxicity resolves.

For subjects who develop grade 2 events following study drug injection, the subject should be reevaluated closely until the AE returns to Grade  $\leq 1$ , at which time study treatment may be reintroduced at the discretion of the site Investigator. If the *same* Grade 2 AE recurs following the next administration of study drug, study treatment must be permanently discontinued. Subjects experiencing Grade 3 AEs requiring permanent discontinuation of study treatment should be followed closely for resolution of the AE to Grade  $\leq 2$  and the team leadership must be notified.

Subjects with Grade 3 asymptomatic laboratory abnormalities in cholesterol, creatine kinase (CK) or triglycerides may continue study treatment.

For grade 4 events permanently discontinue therapy.

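### Protocol 5.2 makes injection-reaction stops a study withdrawal while 9.1.8 makes them a treatment stop, and neither automatically triggers exit assessments, follow-up visits or ART restart

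*Protocol*

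**What the plan says.** Protocol 5.2 (Subject Withdrawal) is worded as an obligation: "subjects WILL be withdrawn from the study, in consultation with the Medical Monitor and the Investigator, if any of the following are met". The list that follows includes a Grade 2 injection-related event recurring at two consecutive visits, any Grade 3 injection-related event, withdrawal because of an adverse event, and pregnancy.

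Protocol 9.1.8 (SC Injection-related Events) deals with the same injection events as reasons to stop the drug. If the same Grade 2 event "recurs following the next administration of study drug, study treatment must be permanently discontinued". For Grade 3 it speaks of events that require permanent discontinuation and asks for close follow-up until they settle. For the most severe events: "For grade 4 events permanently discontinue therapy". Where a subject chooses to stop after a Grade 1 or first Grade 2 event, the site should "encourage the subject to complete any remaining study visits until the toxicity resolves". Leaving the study is not mentioned.

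What happens after an early stop is set elsewhere, by reference to 5.2.1. The Note in Protocol 4.2 says that subjects who meet a 5.2.1 criterion other than virologic failure "will undergo T48 Visit assessments and enter the Follow-up Phase of the study". ART is re-initiated early under 4.2 "Anytime during the Treatment Phase, if virologic failure occurs or have met any other criteria for discontinuation of study treatment as specified in" 5.2.1, and 7.5.1 permits ART during the Treatment Phase "if virologic failure occurs or if subject meets any other criteria for discontinuation of study treatment as specified in" the same section. The 5.2.1 list has five items: virologic failure; an AIDS-defining condition or need for prohibited medication; clinically significant immunosuppression; a wish by the subject or clinician to restart ART; and pregnancy.

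**The concern.** A subject taken off PRO 140 by a mandatory safety rule has no exit path of their own, while a subject who simply wishes to restart ART does. These subjects gave up suppressive ART to enter the study. Section 1.3 reports that in earlier studies viral load returned to pre-dose levels as PRO 140 was cleared. The period just after the drug is stopped is therefore when ART resumption and a viral load check matter most.

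The loss would also be selective, falling on the subjects who tolerated the drug worst. Appendix III does not reserve the triggers for rare events: Grade 2 includes bleeding that exceeds the bandage and stops by itself, or leakage that stops with slower injection. Section 6.2 expects the larger 1.5 mL and 2 mL injections to be uncomfortable for some subjects with low body fat. Losses could thus differ by dose, although the documents give no rates to show it.

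**Working it through.** This is a check of text against text. No planned figure has to be reproduced.

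**Step 1. Each event in the three sections.**

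| Event | 5.2 | 9.1.8 | Listed in 5.2.1? |
|---|---|---|---|
| Recurrent Grade 2 injection-related AE | Withdraw from study | Stop treatment permanently | No |
| Grade 3 injection-related AE | Withdraw from study, any occurrence | Follow closely, for events requiring a permanent stop | No |
| Grade 4 | Not named; only the general AE item could apply | Stop therapy permanently | No |
| Other AE-driven withdrawal | Withdraw from study | Subject's own choice to stop: encourage remaining visits | No |
| Pregnancy | Withdraw from study, follow to term | Not addressed | Yes |

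Two mismatches follow. Sections 5.2 and 9.1.8 differ on whether the subject leaves the study or only stops the drug. They also differ on Grade 3, where 9.1.8 can be read as covering only a subset of events.

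**Step 2. What hangs on the 5.2.1 list.** Three things do: T48 assessments with Follow-up Phase entry (4.2, Note), early ART re-initiation (4.2), and permission for ART during the Treatment Phase (7.5.1). The first four rows of the table have no 5.2.1 entry of their own.

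**Step 3. What is at risk per affected subject without virologic failure, if a site acts on 5.2 alone.**
- HIV-1 RNA: exit T48 assessment + NVF-FU1 + NVF-FU2 = 3 results (7.10.9, Table 4-3a).
- CD4: the same three visits = 3 results.
- ECG: scheduled at screening and then at T48 or the VF visit (7.7), so 1 of 1 post-baseline recording.
- Weight: scheduled at screening, T48 and VF (7.9), so 1 of 1 post-baseline value.

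ECG and weight changes are primary safety measures (8.2.1). SAP 7.3 imputes nothing, and SAP 7.5.5 censors subjects who withdraw without virologic failure at early termination.

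**Step 4. Do the two follow-up visits cover drug washout?** This is illustration only, because the documents give no half-life for repeated SC dosing in humans. Assume first-order decline and count days from the last dose, with the exit assessment at about that time. The fraction remaining is 2^(−t / half-life).
- Half-life 3.5 to 3.9 days (single IV dose, Protocol 1.4.2.4). Day 14: 2^(−14/3.5) = 6.25% and 2^(−14/3.9) = 8.3%. Day 28: 0.39% and 0.69%.
- Half-life about 200 hours (monkeys, IV and SC, Protocol 1.4.1), or 200/24 = 8.3 days. Day 14: about 31%. Day 28: about 10%.

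The range is 6% to 31% at two weeks and 0.4% to 10% at four weeks. On any of these values the visits fall while drug is being lost. The timing of rebound cannot be read from them: Protocol 1.4.2.5 reports high receptor occupancy for 29 days after single IV doses. The point does not depend on this step.

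**The case against.** The strongest reply is that a route already exists. A subject stopped for an injection reaction is off ART and has lost the only active drug, so the subject or clinician will nearly always wish to restart ART. That is a 5.2.1 criterion, and the exit assessment and follow-up visits then apply. Section 5.2.2, written for withdrawn subjects, asks sites to go on following those off treatment whenever possible and to make every attempt to collect follow-up information. Extra RNA draws are allowed (4.2), and AE, SAE and pregnancy follow-up continues (5.2, 9.1.1, 9.2.2). Withdrawal is also partly a disposition label. Under 5.1, "A subject who completes the 48-week Treatment Phase and 4-week Non-Virologic Failure Follow-Up Phase will be considered as having completed the study", with a separate definition for subjects with virologic failure, and 5.2 counts anyone who enters treatment and meets neither as prematurely withdrawn.

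Much of this stands. A reader might infer that the protocol bars these subjects from ART or follow-up. It does not: the 7.5.1 restriction concerns the Treatment Phase, and the restart-ART item is open to them. A reader might also infer that 5.2.1 only stops the drug, but it recommends ART resumption as well. And pregnancy might look like a full conflict, yet 5.2.1 already routes it, and stopping the drug, exit visits, follow-up to term and a withdrawn disposition can coexist.

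The reply does not supply an automatic trigger. The restart-ART item depends on a stated wish rather than on the event. The 5.2.2 sentence about staying in the study is only a suggestion, and following subjects per protocol leads back to the 4.2 Note, which does not name them. The firm instruction in 5.2.2 for AE withdrawals points to AE and SAE reporting, not to viral load, CD4, ECG, weight or ART.

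**Conclusion.** The inconsistency between 5.2 and 9.1.8 is real, and the exit path for injection-reaction, Grade 4 and AE-driven stops is usual rather than guaranteed. If a site relies on 5.2 alone, the exposure per affected subject without virologic failure is up to three HIV-1 RNA and three CD4 results plus the single scheduled post-baseline ECG and weight. The number of such subjects cannot be derived. Earlier SC experience describes reactions as mild (1.4.2.2, 1.4.2.6), but at doses below 525 mg and 700 mg.

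A reader might go further and infer bias in the trial's efficacy comparison. The documents do not support that: SAP 7.3 and 7.4 plan no inferential statistics, and nothing shows how often the triggers will be met or whether they differ by dose. Pregnancy is a minor wording inconsistency. This is a cheap improvement that serves subject safety and the sponsor's stated aim in 5.2.2 of minimising missing data.

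**What to change.** - **Section 5.2:** reword the injection-reaction, AE-driven and pregnancy triggers as discontinuation of study treatment. Split the item that joins the subject's own choice with AE withdrawal, so that only the choice to leave remains study withdrawal. The non-compliance item can stay as it is.
- **Section 5.2.1:** add recurrent Grade 2, Grade 3 and Grade 4 injection-related events and AE-driven discontinuation. Introduce them with *must*, separately from the items that are only *recommended*; otherwise mandatory stops would sit under softer wording and create a new mismatch. State that ART resumption, T48 assessments and NVF-FU1/NVF-FU2 apply.
- **Section 9.1.8:** align the Grade 3 wording with 5.2, so that it is clear that any Grade 3 injection-related event stops treatment.

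The cost is protocol wording, plus one exit assessment and two already-defined visits per affected subject. No other stopping threshold and no planned analysis changes.

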### 5.2.1 Discontinuation of Study Treatment

Discontinuation of study treatment (PRO 140) and resumption of previous or alternative antiretroviral regimen is recommended if:

- Subject experiences virologic failure (defined as two consecutive HIV-1 RNA levels of  $\geq 200$  copies/mL).

**Note:** *Subjects in Group A that experience virologic failure have option of re-initiating ART regimen or participating in Part 2 of Treatment Phase and receive higher dose of PRO 140 (525mg SC) weekly injection for remainder of 48-week Treatment Phase or until subsequent virologic failure event after viral re-suppression on higher dose.*

*Subjects in Group B that experience virologic failure have option of re-initiating ART regimen or participating in Part 2 of Treatment Phase and receive higher dose of PRO 140 (700mg SC) weekly injection for remainder of 48-week Treatment Phase or until subsequent virologic failure event after viral re-suppression on higher dose.*

- Develops AIDS-defining conditions as specified in Appendix I ([Section 17.1](#)) under which subject is unable to continue treatment with study drug (PRO 140), or subject require treatment with prohibited concomitant medications.
- Shows signs or symptoms of clinically significant immunosuppression
- Subject or the subject's clinician wishes to restart ART.
- Subject becomes pregnant.

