#### 7.10.12 HIV-1 Drug Resistance Assay

a. GenoSure Archive Assay

GenoSure Archive assay provides HIV-1 antiretroviral drug resistance data when standard resistance testing cannot be performed due to inadequate plasma viral load.

- Frequency of sample collection: At SV, T1, and T48. Additionally, at VF, VF-6mFU and VF12mFU Visits, if last known HIV-1 RNA level is <1000 copies/mL.

b. PhenoSense® GT

PhenoSense® GT is a combination resistance test for three classes of antiretroviral drugs (i.e., nucleoside/nucleotide, non-nucleoside, and protease inhibitors), that provides both phenotypic and genotypic results from the same blood sample (viral load  $\geq 500$  copies/mL).

- Frequency of sample collection: At VF, VF-6mFU and VF12mFU Visits, if last known HIV-1 RNA level is >1000 copies/mL.

c. PhenoSense Integrase and GeneSeq Integrase testing

PhenoSense Integrase and GeneSeq Integrase testing will be additionally performed in conjunction with PhenoSense® GT, if subject has past exposure to an integrase or in cases where complex drug resistance patterns is known or suspected.

*Samples for PhenoSense® GT (and PhenoSense Integrase and GeneSeq Integrase testing, if collected) will be stored at Lab and will be analyzed only if subject experiences virologic failure.*

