7.3 Handling of Missing Data

There are no inferential statistics planned for this study, hence all data will be presented without imputation.

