7.5.4 Virologic Failure

Virologic failure is defined as two (2) consecutive plasma HIV-1 RNA levels of ≥ 200 copies/mL.

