8.2.2.1 Proportion of participants experiencing virologic failure at the assigned dose

The percentages of subjects with virologic failure (as defined in [Section 7.5.6](#)) will be presented descriptively by treatment groups for the ITT and PP populations.

Note: Assigned dose refers to the dose allocated at the time of randomization/enrollment.

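### A subject who restarts ART after a single HIV-1 RNA value of 200 copies/mL or more may never be counted as a virologic failure, and the SAP has no rule or supportive analysis for this case

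*Protocol*

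**What the plan says.** - **Endpoint.** SAP 7.5.4: "Virologic failure is defined as two (2) consecutive plasma HIV-1 RNA levels" of at least 200 copies/mL. It does not say whether both values must be drawn on PRO 140 or before ART. SAP 8.2.2.1 reads "The percentages of subjects with virologic failure (as defined in" and goes on to cite Section 7.5.6, which in fact defines re-suppression. The percentages are shown by treatment group for ITT and PP.
- **Stopping PRO 140.** Protocol 5.2.1 lists, apart from VF, the case where the subject or "clinician wishes to restart ART". No viral-load condition is attached. The study is open label (Protocol 8.4).
- **What follows.** The Note in Protocol 4.2 covers this group: "Subjects who meet any criteria (other than virologic failure) for discontinuation of study treatment as specified in" Section 5.2.1 have the T48 assessments and then enter follow-up. An extra RNA draw between visits is optional.
- **Missing data.** SAP 7.3: "There are no inferential statistics planned for this study, hence all data will be presented without imputation". Protocol 8.6.4, by contrast, promised imputation methods in the SAP for the ITT analyses.
- **Time to VF.** SAP 7.5.5 censors subjects without an event at the last visit or at early termination.
- **Resistance testing.** Under Protocol 7.10.12, stored PhenoSense GT and integrase samples "will be analyzed only if subject experiences virologic failure".

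**The concern.** ART suppresses the event being counted. If it starts after one high value, the next RNA may be below 200 because of ART, and a subject who was rebounding on PRO 140 never meets the definition. Neither the protocol nor the SAP says how to classify that subject.

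No tests are planned, so the plain percentages by dose, together with time to VF, are what readers will use to judge the doses. An error from this route goes one way only, toward fewer failures. It could also differ between groups. Staff and subjects know the dose, and confirmed failure opens a higher PRO 140 dose to Groups A and B but not to Group C, so the reason to wait for a second value is not the same.

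The SAP already recognises loss of suppression short of VF in one place: its definition of rescue in 3.1.2 includes subjects who could not maintain suppression and moved to a higher PRO 140 dose. Rescue by ART has no counterpart.

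**Working it through.** The plan gives no failure rate, restart rate or power figure, so there is nothing of its own to reproduce. The check traces one subject through the text and then shows the effect over assumed ranges.

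**1. Trace of a subject with one value of 200 or more.**
- One value is not VF (SAP 7.5.4).
- The subject or clinician chooses ART (Protocol 5.2.1). Neither 5.2.1 nor the 4.2 Note requires an RNA sample before ART resumes.
- The T48 assessments include RNA (Protocol 7.10.9), and RNA is drawn again at 2 and 4 weeks (Protocol Table 4-3a). The text does not say whether the T48 sample comes before or after the first ART dose.
- If the next value is 200 or more, the definition is met as written, because the SAP does not exclude values drawn on ART.
- If the next value is below 200 or missing, VF is not met. The ITT population is everyone enrolled or randomized and dosed (SAP 6.1), and nothing is imputed (SAP 7.3). The subject therefore sits in the denominator without an event and is censored in time to VF.

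The last step is an inference from the definition, the population and the no-imputation rule. No sentence states the coding.

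**2. Is there time to restart before confirmation?** RNA is scheduled every two weeks to week 16, then nominally every four weeks. From the visit windows in Protocol Table 4-2:
- shortest gap between adjacent windows, T21 to T22: 22 − 21 = 1 week
- longest gap, T18 to T25: 25 − 18 = 7 weeks
- T42 to T48: 48 − 42 = 6 weeks

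The longer gaps are window extremes, not typical intervals.

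**3. Size, by assumption.** Let p be the proportion who would fail if every failure were confirmed, and q the share of those who restart ART first and never get a second value of 200 or more. Reported proportion = p(1 − q); shortfall = p × q.
- p = 0.40, q = 0.05: 0.40 × 0.95 = 38%
- p = 0.40, q = 0.10: 0.40 × 0.90 = 36%
- p = 0.40, q = 0.25: 0.40 × 0.75 = 30%
- Wider range, p from 0.30 to 0.60 and q from 0.05 to 0.20: shortfall from 0.30 × 0.05 = 1.5 points to 0.60 × 0.20 = 12 points

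Planned enrolment implies A = 150 + 75 = 225, B = 75 + 100 = 175 and C = 100. The wider range is then 1.5 to 12 subjects in Group C, and 175 × 0.015 = 2.6 to 175 × 0.12 = 21 in Group B.

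**4. If q differs by group.** With the same true 40%, q = 0.10 in one group and 0.25 in another gives 36% against 30%, an apparent difference of 6 points. For scale, the 95% half-width for one group of 100 at 40% is 1.96 × √(0.40 × 0.60 / 100) = 9.6 points.

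**5. Does the category occur?** Protocol 1.4.2.8 (CD01-Extension, with a 400 copies/mL threshold) reports 5 failures among 16 eligible subjects and, separately, one withdrawal for restarting ART at week 99. That is 5/16 = 31.3% as counted, and 6/16 = 37.5% if the restart were counted. The viral load at that restart is not given, so this shows only that such subjects are listed apart from failures.

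**The case against.** A reader might infer that every early restarter is coded a non-failure and that the VF proportion is certainly understated. The documents do not support that. The T48 and follow-up samples can supply the second high value, and Protocol 4.2 lets a subject stay on PRO 140 while a new regimen is put together, so ART need not come before the next draw. Some single values would not have been confirmed anyway. This stands, and it makes the claim conditional.

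A reader might also infer that resistance data are lost for these subjects. That is too broad. GenoSure Archive, PhenoSense Entry and Trofile DNA are all done at T48. Only PhenoSense GT/Integrase and the 6- and 12-month visits are tied to VF. Under Protocol 7.10.12, a VF subject whose last RNA is below 1000 copies/mL would have GenoSure Archive in any case.

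The primary list also includes completing 24 and 48 weeks with RNA below 50 copies/mL. A subject who stops early for ART cannot be a 48-week success there. Discontinuation reasons and ART re-initiation are summarised and listed as well. This is a partial offset: it does not repair the VF proportion or time to VF, and no planned table links the ART start to the last RNA value.

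Finally, no inferential comparison is planned, Protocol 5.2.2 asks investigators to contact the medical monitor before stopping treatment, and different restart behaviour by dose is conjecture. All true. No error rate or power is affected. The descriptive percentages are still open to the shift.

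**Conclusion.** The gap is real in a conditional form. A subject who restarts ART after one value of 200 or more, and whose next value is below 200 or missing, drops out of the VF count by default and is censored in time to VF. The proportion may be understated, possibly unequally across dose groups, and cannot be overstated by this route.

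The size is unknown. The 38% to 30% illustration rests wholly on an assumed 40% true failure and an assumed 5% to 25% never confirmed; the wider assumed range gives 1.5 to 12 points. That the bias differs by dose is possible from the design but not shown.

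It might also seem to follow that the primary definition should be changed. It does not: the two-value rule is fixed in the protocol, roughly 300 subjects were enrolled open label before the current stage, and recoding single values as failures would bring blips into the primary result. A pre-specified supportive analysis is enough. This should be fixed, but it does not undermine the trial.

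**What to change.** 1. Keep two consecutive values as the primary definition. Correct the cross-reference in SAP 8.2.2.1 from 7.5.6 to 7.5.4.
2. In SAP 8.2.2.1 and 8.2.2.2 add a pre-specified supportive analysis. Count as failure at the assigned dose any subject who starts ART before the planned end-of-treatment overlap when the last RNA before ART was 200 copies/mL or more, with the event dated at that value. Report the number of such subjects by dose group. For these subjects, the strict and supportive rows then bracket the result.
3. State in SAP 7.5.4 whether a value drawn after ART restart can confirm VF. The same sentence settles a first high value at T48, which can only be confirmed on ART because ART resumes one week before the end of treatment.
4. Reconcile the two statements in SAP 7.5.5 on the date of failure (the text uses the second value, the formula the first), and reconcile Protocol 8.6.4 with SAP 7.3 on imputation.
5. Ask the sponsor to reconcile Protocol 5.2.1, the 4.2 Note and the VF-visit provisions in 4.3 for subjects with an unconfirmed high value. Which path they follow, and when ART restarts, is for the sponsor and investigators.

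**Cost.** SAP wording and one supportive row, from ART dates and RNA values already collected. The downside is that a few transient blips count as failures in the supportive row.
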